Exposure to RPV will be determined by the presence of prescription records for the FDC of FTC/RPV/TDF or single agent of RPV among patient data. Relevant drug codes will be used to identify RPV-containing regimens in the HIV cohorts. The baseline date for exposure follow-up (index date) for a patient within a given treatment group will be defined by first prescription of RPV or EFV-containing regimens. Duration of exposure will be based on dispense date and days of supply for each dispensed prescription. Exposure to RPV or EFV-containing regimens will be considered discontinued if the prescription is not refilled within a specified interval of time (e.g. twice the days' supply) of the previous prescription. Switches from one drug to another will be captured and time on drug will be defined by the exposure periods. The total length of exposure to a given drug will be the time between start and stop periods of exposure to the same drug.

4.2.1.1. **Exposure Definition in Nested Case-Control Study**

For the nested case-control analysis, exposure will be based on 1) level of daily medication adherence, and 2) level of adherence to food recommendations. Cases and matched controls that are selected will be asked to retrospectively report via a questionnaire how often they took their HIV medication during a specified time period and how often RPV was taken with food. A single item querying the number of prescribed doses the participant had missed in a specified time period will be used, as follows:

"How many doses of your complete HIV regimen did you miss in the last 7 days?"

"For those days you missed, what component of your HIV regimen did you miss?" (If applicable)

"How often did you take RPV with food in the last 7 days?"

Since RPV dosing is once-daily, number of doses taken is equivalent to number of days the medication is taken. A 7-day recall period is proposed for this analysis as it has the advantage of including a weekend, during which adherence is often problematic. Further, DATE (6 September 2011) 20

longer recall periods (7-day vs. 1-3 day) may yield more useful data for once-daily ART dosing since there are too few dosing times in a very brief recall period to capture variations in adherence behaviors (Simoni, 2006).

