4.2.2. Outcome Definition and Measures

Outcome definitions for the DUS will include:

- HIV viral load prior to initiating RPV-containing regimens or EFV-containing regimens as well as over the course of therapy
- Virologic failure defined for treatment naïve patient as plasma HIV-1 RNA levels >500 copies/ml after 6 months of regimen initiation if baseline viral load is >500 copies/ml. For patients undetectable at baseline virologic failure is defined as 2 consecutive plasma HIV-1 RNA levels >500 copies/ml after starting the regimen.
- HIV treatment status (naïve/experienced) at RPV or EFV treatment initiation
- Prior use of ARV treatment, if any
- NNRTI drug resistance at RPV or EFV treatment initiation as well as over the course of therapy
- Proportion of patients who have resistance testing prior to initiating RPV or EFV therapy as well as over the course of therapy

- Concomitant medications prior to initiating RPV or EFV therapy as well as over the course of therapy
- Comorbidities prior to initiating RPV or EFV therapy as well as over the course of therapy
- Reason for discontinuation of RPV or EFV-containing products
- Reason for switch of ARV treatment
- Adverse events over the course of RPV or EFV therapy

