4.2.3. Case Definition for Nested Case-Control Study

Cases will be selected based on occurrence of virologic failure as defined in the DUS, and controls will be selected based on absence of virologic failure.

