4.2.5. Length of Follow-up

Each patient will be followed for 12 months from the initiation of RPV or EFVcontaining regimens, or until death, loss to follow-up within the cohort, or virologic failure, whichever occurs first. Time varying variables will be recorded at each patient visit.

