4.5.3. Additional analysis on virologic failure and emergence of resistance

Additional analyses will be conducted to evaluate outcomes within twelve months of initiating RPV or EFV-containing regimens. Specific analyses to be conducted are as follows:

- The proportion of patients with virologic failure within twelve months of RPVcontaining regimens initiation or EFV-containing regimens initiation
- The proportion of patients with treatment emergent RPV or EFV RAMs within 12 months of NNRTI initiation

The decision to prescribe RPV-containing regimens or EFV-containing regimens will be influenced by the treatment recommendations, patient characteristics, the prescriber assessment of the health status and risk profile, and the local policies and formularies. Thus, when planning to compare rates of virologic failure and emergence of resistance, it will be important to first determine whether the populations are comparable. The parameters available in the HIV cohorts will be used to investigate the relative importance of patient characteristics or risk factors that may be used to identify which patients are selected to receive RPV-containing regimens compared with EFV-containing regimens.

The evaluation of appropriateness of a comparison of RPV-exposed patients with EFVexposed patients will be based on the consistency of the clinical experience of the two treatment groups. This assessment will be conducted based on distribution of propensity scores for receipt of RPV-containing regimens or EFV-containing regimens.

The evaluation of clinical experience will assess the patients' clinical and demographic characteristics in relation to receipt of RPV or EFV-containing regimens. Information will be captured on the patients' clinical and demographic characteristics that could be predictive of RPV treatment appropriateness. This information will be incorporated into multivariate models to identify a group of patients with similar characteristics to the RPV-containing regimens cohort but treated with EFV-containing regimens. All patients

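### Virologic failure is defined by viral load alone, so a patient switched for virologic reasons before the rule is met, and then suppressed, is never counted as a failure.

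*Protocol*

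**What the plan says.** Section 4.2.2 gives two limbs for virologic failure. For a treatment-naive patient it is "plasma HIV-1 RNA levels >500 copies/ml after 6 months of regimen initiation if baseline viral load is >500 copies/ml". The other limb is "For patients undetectable at baseline virologic failure is defined as 2 consecutive plasma HIV-1 RNA levels >500 copies/ml after starting the regimen". Neither mentions stopping or changing the drug. The reasons for discontinuation and for switching ("Reason for switch of ARV treatment") are separate items in the same outcome list and do not feed into failure.

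Section 4.2.5 follows each patient for 12 months "or until death, loss to follow-up within the cohort, or virologic failure, whichever occurs first". A switch is not among the end points. Section 4.2.1 uses switches only to bound exposure: "Switches from one drug to another will be captured and time on drug will be defined by the exposure periods".

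The definition is then used in three places:

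- Section 4.5.3 reports "The proportion of patients with virologic failure within twelve months of RPVcontaining regimens initiation or EFV-containing regimens initiation".
- The same section computes incidence rates as events over total person-exposure time, with relative risks and Poisson models for RPV against EFV.
- Section 4.2.3 carries it into the nested study, where meeting the definition makes a patient a case and controls are those who have not met it.

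**The concern.** Clinicians change a regimen when viral control is poor or lost. If that happens before the viral-load rule is satisfied and the new regimen works, the action removes the event being counted. Describing virologic failure is a primary objective (1.3.1), and the same definition drives the RPV/EFV comparison and the selection of nested cases. One gap therefore touches three results: the absolute failure risk, the relative risk, and the number of cases available for the adherence and food analysis. Nothing in the protocol treats a virologic switch as failure or examines what happens if it is.

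**Working it through.** **1. Does the text produce the gap?** Two illustrative patients:

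- Undetectable at RPV start, 2,000 copies/ml at month 4, switched on that result, undetectable at month 6. There is no second consecutive value above 500, so no failure.
- Treatment-naive with 80,000 copies/ml, below 50 at month 2, 4,000 at month 4, switched, below 50 at month 7. There is no value above 500 after 6 months, so no failure.

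The gap is wider under the naive limb, because nothing before 6 months can count. Under the other limb it lies between the first and second raised value.

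**2. What happens in each analysis?**

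- 12-month proportion (4.5.3): the patient is in the denominator and not in the numerator.
- Rate (4.2.1 with 4.5.3): exposure time stops around the switch and no event is recorded. The patient is censored for a reason tied to the outcome.
- Nested study (4.2.3): the patient cannot be a case.

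**3. The plan's own figure that depends on the failure count.** Table 1 in 4.1.2 gives power 0.828 for 40 cases at odds ratio 3.0 (4:1, two-sided 5%, exposure 50%). Check: exposure in cases = 3 × 0.5 / (0.5 + 3 × 0.5) = 0.75. A two-proportion test with pooled variance, 40 cases and 160 controls, gives 0.837. For 90 cases at odds ratio 2.0 it gives 0.820 against the stated 0.816. Both agree closely enough to use the method below.

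**4. Illustrative size.** The protocol gives neither an expected failure risk for this study nor a switch rate. Assumptions: true 12-month failure risk F of 5% to 20%, and a share m of 10% to 50% of failures that are switched before the rule is met and then suppress. Group size is 600 (2.1).

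Observed risk = F × (1 − m):

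| F | true failures | m = 10% | m = 30% | m = 50% |
|---|---|---|---|---|
| 5% | 30 | 27 (4.5%) | 21 (3.5%) | 15 (2.5%) |
| 10% | 60 | 54 (9%) | 42 (7%) | 30 (5%) |
| 20% | 120 | 108 (18%) | 84 (14%) | 60 (10%) |

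Relative risk when the truth is 1.0 = (1 − m for RPV) / (1 − m for EFV):

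- 30% on RPV, 10% on EFV: 0.70 / 0.90 = 0.78
- 10% on RPV, 30% on EFV: 0.90 / 0.70 = 1.29
- equal shares: 1.0

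The rate behaves in the same way. With a constant hazard and F = 10%, the true rate is −ln(0.90) = 0.105 per person-year. With person-time ended at the switch, the observed rate is 0.105 × (1 − m): 0.095 at m = 10% and 0.074 at m = 30%, again a ratio of 0.78.

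**5. Nested study.** If 60 true failures on RPV (F = 10%) fall to 48, 42 or 30 cases (m = 20%, 30%, 50%), power at odds ratio 3.0 falls from 0.955 to 0.900, 0.855 or 0.712.

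**The case against.** A viral-load-only endpoint is legitimate, and arguably prudent, where switch reasons are recorded inconsistently, as section 5 concedes. Requiring two consecutive values deliberately sets aside an isolated rise, so the first illustrative patient may be exactly whom the rule means not to count. Reasons for switching and viral load over time are already to be reported by group (1.3.2), so early virologic switching would be partly visible. A sensitivity analysis might also be placed in a separate analysis plan.

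Much of this stands as a reason to keep the present definition. It does not close the gap. A descriptive table of switch reasons does not change the failure proportion or rate, and the second patient is missed even though control was clearly lost.

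Three stronger readings are tempting and are not supported:

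- *That RPV is made to look better than EFV.* The protocol says nothing about which group would be switched sooner. The bias could run either way or be absent. A raised value after the switch might also be charged to the first drug, which would work in the opposite direction.
- *That the new drug's success is credited to the first drug throughout.* That describes the 12-month proportion. In the rate, time after the switch is not time on the index drug, and the problem is informative censoring.
- *That these patients are misclassified as controls.* Controls are sampled from RPV-treated patients at risk when the case occurs (2.1.1). Before the switch such a patient is a valid control, and afterwards the question about taking RPV with food in the last 7 days (4.2.1.1) could hardly be answered. Loss as a case is established; misclassification as a control is not.

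**Conclusion.** The point holds in limited form. As written, 4.2.2, 4.2.5 and 4.5.3 leave uncounted any virologic switch made before the rule is met and followed by suppression, so absolute failure is understated in a primary outcome whenever such patients exist. How much cannot be computed from the protocol; the tabulated figures rest wholly on assumed values of F and m. Bias in the RPV/EFV relative risk is conditional on the groups differing in early virologic switching, and its direction is unknown. The nested study loses cases, and hence power, to the same unknown degree. This is a worthwhile, inexpensive improvement to the outcome definition; it does not show that the planned comparison is invalid.

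**What to change.** - Keep the viral-load-only definition in 4.2.2. Beside it, for both groups, report a composite in which stopping or switching the index NNRTI with a recorded reason of virologic failure or inadequate response counts as failure, dated at the switch.
- State whether viral loads measured after the switch count towards failure, and apply the same rule to the 12-month proportion and to the rate.
- Add a sensitivity analysis for switches whose reason is missing or unclear and whose last on-drug viral load exceeded 500 copies/ml. Do not count switches recorded as non-virologic, such as for an adverse event; otherwise one unconfirmed value followed by a stop for any reason would become a failure.
- Use the composite as a sensitivity case definition in the nested study.

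The cost is some protocol wording and a few programmed rules on data that 4.2.2 already lists. The downside is that inconsistent switch reasons (section 5) will misclassify some patients, possibly differently between cohorts. Reporting both definitions shows how far the results depend on this.

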4.2.3. Case Definition for Nested Case-Control Study

Cases will be selected based on occurrence of virologic failure as defined in the DUS, and controls will be selected based on absence of virologic failure.

4.2.4. Potential Confounders and Effect Modifiers

Potential confounders and effect modifiers will be collected from the databases and assessed to determine their association with the outcomes of interest. These covariates will be used to perform adjusted analyses and to describe the treatment groups. Patient factors to be considered will include, but are not limited to, demographics, comorbidities and concomitant medications that might influence appropriate use. Risk factors will be identified in the database using pre-specified diagnosis and/or treatment codes.

- Age
- Sex
- Weight or BMI
- CD4 at treatment initiation and at treatment failure
- Ethnicity
- Route of HIV infection
- Co-infection with hepatitis B/C or TB
- Depression

4.2.5. Length of Follow-up

Each patient will be followed for 12 months from the initiation of RPV or EFVcontaining regimens, or until death, loss to follow-up within the cohort, or virologic failure, whichever occurs first. Time varying variables will be recorded at each patient visit.

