- To describe HIV-treatment regimens and concomitant medications of patients initiating RPV or EFV-containing regimens
- To describe changes in HIV treatment and concomitant medication over the course of RPV and EFV treatment
- To describe reasons for switch of ARV treatment
- To describe adverse events over the course of RPV or EFV treatment

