European HIV cohorts capture care as given and are generalizable to the population likely to be exposed to RPV-containing regimens. The proposed design does not interfere with the physician's decision regarding what to prescribe for the individual patient. Patients receive the drug in everyday practice and are not a highly selected group of patients who may not be representative of the 'real-world' population. The use of multiple cohorts located in several different countries increases the generalizability of the observed rates of use by physicians. The major strength of using the HIV cohorts for a DUS is the protocols for data collection have been specifically designed for HIV research (www.hicdep.com). Data are systematically collected on all clinical aspects salient to HIV care. These data include laboratory variables for HIV viral load, CD4+ counts, drug resistance information, concomitant medications, adverse events, and detailed information on HIV treatment. Additionally, patients are followed in the cohort until death or loss to follow-up from the cohort. Data are collected independent of the proposed DUS and are not subject to physician recall or potential biases involving selfreported drug prescribing or patient management. These data are collected longitudinally and in a time-dependent manner so that variation in time-dependent variables can be assessed. This is particularly important when considering the outcome of virologic failure and potential factors contributing to loss of virologic control. Finally, these data are collected electronically and do not place additional burden on the treating physician or patient.

Additionally, a comparator group of EFV-treated patients will be included in this study to provide contemporary context to utilization and outcomes observed within the RPVtreated group. The EFV-treated group will provide insight into patient characteristics DATE (6 September 2011)

likely to influence health-care providers to channel patients to EFV-containing regimens or to RPV-containing regimens. Additionally, the EFV treatment group will provide a better understanding of the observed rates of virologic failure and prescribing factors observed within the RPV-treated group.

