3. STUDY POPULATION

3.1. Patient Selection

The study population will be drawn from the population of patients enrolled in one or more European HIV cohorts. Eligible patients must be new users of RPV-containing regimens at the initiation of therapy (inception cohort). Patients eligible for the comparator cohort must be new users of EFV-containing regimens. Data will be included for analysis based on the availability of RPV-containing regimens in each country. Patients in the EFV-treated group will be eligible for selection from each HIV cohort if they initiate an EFV-containing regimen after the availability of an RPV-containing regimen is observed within the respective cohort. The study period will start at the date of market availability of RPV-containing regimens in the participating counties and will end when in total 600 patients from each treatment group (RPV and EFV) have been included in the study and followed for 12 months, until virologic failure, or lost to follow-up, whichever occurs first.

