4.5.2. Analysis of Appropriate Use

This analysis will describe and summarize the prescribing of RPV and EFV-containing regimens. The analysis will ascertain the number of patients exposed to RPV-containing regimens and EFV-containing regimens. The prescriptions will be summarized by patient demographics (age, sex, geography) and clinical characteristics (comorbidities and concomitant medications). In addition, the details of RPV and EFV-containing regimens use patterns will be described including duration of use, persistence of therapy, and usage of other HIV treatments.

This analysis will describe and summarize the utilization patterns of RPV-containing regimens and EFV-containing regimens with respect to viral load, CD4 counts, pretreatment RPV-containing regimens resistance testing, adverse events, HIV treatment status (naïve/experienced), prior HIV treatment regimens, concomitant medications, comorbidities, and route of infection. The analysis will ascertain the number of patients initiating RPV-containing regimens and the proportion of patients treated in accordance with RPV products' SmPC. Proportions will be estimated separately for each recommendation of patient treatment. The denominator for each proportion will consist of the number of all patients initiating RPV-containing regimens included in the study. Proportions will be estimated separately using the following numerators:

- The number of patients naïve to HIV treatment regimens
- The number of patients with documented pre-treatment screening for ARV RAMs

• The number of patients initiating RPV-containing regimens with a baseline viral load ≤ 100,000 HIV-1 ribonucleic acid (RNA) copies/mL

Proper prescribing will be summarized by patient demographics and potential confounders.

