7.2. Study Completion/Termination

7.2.1. Study Completion

The study will be completed once a minimum of 600 patients have entered each of the RPV and EFV treatment groups and have been followed individually for 12 months from RPV or EFV-containing regimen initiation, death, virologic failure, or loss to follow-up to the HIV cohort, whichever comes first. Interim analyses will be conducted to check the number of RPV-treated patients captured in the DUS and to review the estimated timeframe that will be needed to obtain the required sample size. Updates on patient accrual and timelines for study completion will be provided as part of Periodic Safety Update Reports (PSURs) and Risk Management Plan (RMP) updates. A descriptive report on patient counts and the safety profile of RPV-containing regimens with respect to appropriate use by prescribers and patients will be prepared in alignment with the PSUR schedule.

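### Follow-up stops at virologic failure for every outcome, so treatment changes made after and because of failure fall outside the switch, discontinuation and persistence results

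*Protocol*

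**What the plan says.** Section 4.2.5 sets patient-level follow-up at 12 months from starting RPV or EFV, "or until death, loss to follow-up within the cohort, or virologic failure, whichever occurs first". Two other sections use the same stop to define when the study ends. Section 3.1 (repeated in the synopsis) has patients "followed for 12 months, until virologic failure, or lost to follow-up, whichever occurs first". Section 7.2.1 counts 12 months from "RPV or EFV-containing regimen initiation, death, virologic failure, or loss to follow-up to the HIV cohort, whichever comes first".

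The protocol also promises several outcomes that concern what happens to treatment:

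- Section 1.3.2: "To describe changes in HIV treatment and concomitant medication over the course of RPV and EFV treatment", and "To describe reasons for switch of ARV treatment". Adverse events over the course of treatment are a further secondary objective.
- Section 4.2.2: "Reason for discontinuation of RPV or EFV-containing products".
- Section 4.5.2: "use patterns will be described including duration of use, persistence of therapy, and usage of other HIV treatments".

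Section 1.3.2 adds that secondary objectives are reported by group and for RPV relative to EFV. On the data source, section 2.2 says that "patients are followed in the cohort until death or loss to follow-up from the cohort".

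**The concern.** Stopping at failure suits a time-to-failure rate. It does not suit outcomes that describe why and when patients leave a drug, because a change made in response to failure normally follows the result that defines failure. Suppose a patient with a baseline viral load above 500 copies/ml has 3,000 copies/ml at month 8. That is failure, and follow-up ends. If the regimen is changed at month 9 with failure as the recorded reason, that change lies outside the window. A change for intolerance at month 9 in a patient who has not failed lies inside it.

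The loss therefore falls on one category of reason. A patient who fails and stays on the drug also has later adverse events and the eventual stop date cut off. At stake are the mix of switch and discontinuation reasons, the persistence estimate, and the planned comparison of both between RPV and EFV.

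**Working it through.** The protocol gives no figure for this point, so there is nothing to reproduce. The check has two parts.

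**1. Is any outcome exempt from the stop rule?** Section 4.2.5 is general and names no outcome. Section 4.2.1 says switches will be captured and time on drug defined by exposure periods, but it does not extend the window past failure. Section 5 warns that switch reasons may be recorded inconsistently across cohorts, and does not mention truncation at failure. No section continues observation after failure for any outcome.

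For persistence, a patient who fails while still on the drug leaves observation at that moment. If this is treated as non-informative censoring, the patient is assumed to have the same later chance of stopping as those who have not failed. A patient who has just failed is more likely to change, so persistence is overstated.

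**2. How large could the effect be?**

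Inputs:
- Group size 600 (protocol minimum).
- Failure rate r = 0.05 to 0.35 per person-year. The upper value is the EFV rate in an older cohort study cited in section 1.1; that reference's title describes mainly antiretroviral-experienced patients. The lower values are assumptions.
- s = share of failing patients who switch because of failure within 12 months: 50–80% (assumption).
- O = switches for other reasons per 600: 60–120 (assumption).
- e = share of failure-driven switches made on or before the protocol failure date: not given, varied from 0 to 0.5.

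Formulas, with a constant rate over the year as a simplification:
- Patients stopped at failure: V = 600 × (1 − exp(−r))
- Failure-driven switches: T = s × V
- Failure share with full 12-month observation: T / (T + O)
- Failure share under the rule: eT / (eT + O)

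Patients whose follow-up stops at failure, per 600:

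| r per year | 0.05 | 0.10 | 0.20 | 0.35 |
|---|---|---|---|---|
| V | 29 | 57 | 109 | 177 |

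One case in full, r = 0.10, s = 0.8, O = 60: T = 0.8 × 57.1 = 45.7. Full observation: 45.7 / 105.7 = 43%. Under the rule: 0% at e = 0; 4.6 / 64.6 = 7% at e = 0.1; 13.7 / 73.7 = 19% at e = 0.3; 22.8 / 82.8 = 28% at e = 0.5.

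Across all the assumed inputs:

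| Observation | Failure share of switch reasons |
|---|---|
| Full 12 months | 11–70% |
| Rule, e = 0 | 0% |
| Rule, e = 0.1 | 1–19% |
| Rule, e = 0.3 | 4–41% |

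Effect on a comparison: take two groups with r = 0.10 and r = 0.20, both with s = 0.8, O = 60 and e = 0.1. T is 45.7 and 87.0. With full observation the shares are 43% and 59%, 16 points apart. Under the rule they are 7% and 13%, about 6 points apart. The switches lost are 0.9 × 45.7 = 41 and 0.9 × 87.0 = 78, so the group with more failures loses more.

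**The case against.** The strongest reply is that many virologic changes would still be counted. Under section 4.2.2, failure in patients with a baseline above 500 copies/ml counts only after six months, so earlier changes for poor response stay in view. So do changes after a single value above 500 in patients undetectable at baseline, who need two consecutive values, and changes made at 500 or below. Experienced patients with a detectable baseline are not clearly covered by the definition at all. This stands. A reader might infer that failure will almost vanish as a recorded reason for leaving RPV or EFV. The protocol does not support that, because it gives no value for e, and zero is only the extreme case.

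A reader might also infer that the study would hide failures on RPV. It would not: failure is a primary outcome, reported by group as a rate and a 12-month proportion and compared between groups. Nor can the 40 and 90 cases in section 4.1.2 be read as expected failures. They are power examples for the RPV-only case-control study.

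It can also be said that sections 3.1 and 7.2.1 only define the end of the study, and that section 4.2.1 plans to capture switches. The first part is right, but section 4.2.5 is enough by itself. If the wording about the course of treatment was meant to override it, the two conflict and need reconciling. Leaving this to an analysis plan is not enough, because the protocol itself fixes the window.

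**Conclusion.** The point holds as a mismatch between one follow-up rule and several secondary outcomes. Followed as written, the rule drops changes made after and because of protocol-defined failure, under-represents failure as a reason for leaving either drug, and censors persistence informatively. Both groups are affected; with similar switching after failure, the group with more failures loses more. The direction follows from the order of events. The size does not follow from the protocol: the ranges shown rest on assumed failure rates, switching after failure, other switches and, above all, the share of failure-driven changes on or before the failure date. The outcomes affected are secondary and descriptive, and what they lose is the link between failure and the later treatment change. The change is worth making because the loss is systematic and avoidable.

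**What to change.** In section 4.2.5, and consistently in section 3.1, section 7.2.1 and the synopsis, let virologic failure end follow-up only for the virologic failure rate and proportion. For treatment changes, switch and discontinuation reasons, duration of use, persistence and adverse events, observe every patient to 12 months from the index date, death or loss to follow-up, regardless of failure. This alters the observation window only, not patient care.

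The cost is protocol wording and a longer data extract for patients who fail. Section 2.2 says the cohorts continue to follow patients and that no added collection is needed except for food intake and adherence. The calendar end should hardly move, since patients who do not fail already need 12 months. Two limits remain: switches after month 12 are still missed, which matters because patients with a baseline above 500 copies/ml can fail only after month 6, and the recording of switch reasons may vary by cohort, as section 5 acknowledges.
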